The overall **follow-up period** among women included in the study is the time between the index date and the exit date. The exit date is the censoring date, as defined according to the following general censoring criteria: initiation of a sixth stimulation cycle (regardless of gonadotropin used for COS), end of the study period, emigration (available for Denmark only), death, hysterectomy, bilateral oophorectomy or diagnosis of breast, ovarian or uterine cancer, whichever occurs first. Moreover, each included stimulation cycle will be followed from the stimulation cycle index date until the date when each outcome is assessed; this date varies between the analyses of different objectives and outcomes (see Section 9.7). For a graphical illustration of the study time periods, see Figure 1. As applicable, diagnosis and procedure codes used to define the censoring criteria are provided in Appendix 3 (Section 14.3.2).

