Date of pregnancy test	Continuous	N/A (used to derive outcome variable)		
Pregnancy test result or indicator for pregnancy	Continuous	N/A (used to derive outcome variable)		
Date of ultrasound	Continuous	N/A (used to derive outcome variable)		
Date of pregnancy loss	Continuous	N/A (used to derive outcome variable)		
Other clinical characteristics				
Height/weight or BMI	Continuous	X	X	
Obesity	Categorical	X	X	
Bariatric surgery	Categorical	X	X	
Smoking status*	Numerical	X	X	

Variable	Measurement scale	Baseline characteristic	Candidate variable for PS	Candidate variable for additional adjustment
Type 1 diabetes mellitus	Categorical	X	X	
Type 2 diabetes mellitus	Categorical	X	X	
Antidiabetic drugs	Categorical	X	X	
History of thromboembolic events	Categorical	X	X	
Use of thrombosis prophylaxis	Categorical	X	X	
Porphyria and other relevant conditions [#]	Categorical	X	X	
History of any cancer	Categorical	X	X	
Medical history, fertility-related				
Number of previous failed COS	Categorical	X	X	
History of failed IUI	Categorical	X	X	
History of COS with a study drug	Categorical	X	X	
History of COS with a non-study drug	Categorical	X	X	
Previous delivery with at least one live birth following IVF	Categorical	X	X	
Parity	Categorical	X	X	
OHSS	Categorical	X	X	
Amenorrhea or oligomenorrhea	Categorical	X	X	
PCOS	Categorical	X	X	
Endometriosis	Categorical	X	X	

Variable	Measurement scale	Baseline characteristic	Candidate variable for PS	Candidate variable for additional adjustment
Female infertility diagnosis	Categorical	X	X	
Female factor infertility*	Categorical	X	X	
Male factor infertility*	Categorical	X	X	
Idiopathic factor infertility*	Categorical	X	X	
Medical history, laboratory test results (value at most recent record on or prior to stimulation cycle index date) [†]				
Anti-Müllerian hormone, pmol/L	Continuous	X	X	
FSH, IU/L	Continuous	X	X	
Thyrotropin, mIU/L	Continuous	X	X	
Prolactin, mIU/L	Continuous	X	X	

BMI: body mass index; COS: controlled ovarian stimulation; FET: frozen embryo transfer; FSH: follicle-stimulating hormone; GnRH: gonadotropin-releasing hormone; ICSI: intracytoplasmic sperm injection; IUI: intrauterine insemination; IVF: in vitro fertilization; IU: international unit; L: liter; mIU: milli-international unit; OHSS: ovarian hyperstimulation syndrome; PCOS: polycystic ovarian syndrome; pmol: picomole; PS: propensity score.

Notes:

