9.7.3.5 Time-to-Live Birth Analysis

TTLB (secondary objective 4) will be analyzed restricting to women who initiated their first-ever stimulation cycle during the study period. As per study design, only the first five stimulation cycles (including all cycles of fresh or frozen embryo transfers) with the same study drug will be considered. The stimulation cycle rank number will be employed as the unit of time. Women will be followed until the first delivery with at least one live birth linked to treatment with the drug of interest, the sixth stimulation cycle, switch to another drug used for COS, diagnosis of breast, ovarian or uterine cancer, death, emigration (Denmark only) or end of study, whichever occurs first.

To estimate the TTLB in the original and IPTW-weighted study cohorts, survival analysis will be performed with the Kaplan-Meier method to estimate the time to the first live birth, expressed as the rank number of the stimulation cycle with the given study drug. The resulting Kaplan-Meier plots together with the estimated mean (with 95% CI) and median (with 95% CI) time-to-events will be presented.

For the comparison of the study cohorts, the time-to-live birth rate ratios adjusted for confounding factors, will be estimated by taking into account the IPTWs and using Cox proportional hazards regression model. The Cox model will be weighted with the IPTWs, and any variables included in the PS that are still unbalanced after weighting will be included as covariates for the Cox model. Additionally, the Cox model may be used to adjust the rate ratios for any other potential covariates that are assessed after the start of the stimulation cycle and hypothesized to be associated with the given study outcomes (see Table 1 in Section 9.3.2).

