[†]Country-specific adaptations may be made at the data permit stage. Conditions defined by ICD-10 codes are considered present if there was a record of a primary or secondary diagnosis in the national (patient) registers (outpatient or inpatient care). Similarly, procedures defined by NOMESCO codes are considered to have been performed if there was a record in the national patient registers (outpatient or inpatient care). Conditions ascertained in the IVF registers (not using ICD-10 codes) are considered present if there was a relevant record in those registers.

*All ICD-10 or procedure subcodes are included.

[#]The DNPR additionally records the gestational age at time of abortion.

[‡]Prior to October 2016, induced abortions were not recorded in the SNPR.

[‡]If costs of healthcare resource utilization are unavailable at the individual-level in the register data, available national and regional cost listings will be used for unit costs for healthcare resource utilization.

14.3.2

Censoring Criteria (Section 9.2.3): Diagnosis and Procedure Codes for Definition

Criterion	Diagnosis/procedure code ⁺	Comment
Death (any cause)	N/A	
Hysterectomy	ICD-10: N99.3, O82.2, Z90.7 NOMESCO procedure codes: LCC*, LCD*, LCH 20	ICD-10: Prolapse of vaginal vault after hysterectomy, delivery by caesarean hysterectomy, acquired absence of genital organ (hysterectomy) NOMESCO procedures: procedures related to partial excision of uterus or total excision of uterus
Bilateral oophorectomy	ICD-10: Z90.7 NOMESCO procedure codes: LAE 20, LAE 21, LAF 10, LAF 11, LAF 30	ICD-10: Acquired absence of genital organ(s) NOMESCO procedures: bilateral oophorectomy, bilateral laparoscopic oophorectomy, bilateral salpingo-oophorectomy, laparoscopic bilateral salpingo-oophorectomy, bilateral transvaginal salpingo-oophorectomy
Breast cancer [#]	ICD-10: C50*	Malignant neoplasm of breast
Ovarian cancer [#]	ICD-10: C56*	Malignant neoplasm of ovary
Uterine cancer [#]	ICD-10: C53*, C54*, C55*	Malignant neoplasm of cervix uteri, malignant neoplasm of corpus uteri, malignant neoplasm of uterus, part unspecified

ATC: Anatomical Therapeutic Chemical; ICD-10: International Classification of Diseases, 10th revision; NOMESCO: Nordic Medico-Statistical Committee.

Notes:

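### The censoring codes in 14.3.2 are wider than the criteria in 9.2.3, and the time-to-live-birth list in 9.7.3.5 does not match them

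*Protocol*

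**What the plan says.** Section 9.2.3 ends a woman's overall follow-up at the first of several events, among them "death, hysterectomy, bilateral oophorectomy or diagnosis of breast, ovarian or uterine cancer, whichever occurs first".

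Appendix 14.3.2 turns these into codes:

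- Hysterectomy is "ICD-10: N99.3, O82.2, Z90.7" together with procedure codes LCC*, LCD* and LCH 20. The comment column describes the last two ICD-10 codes as "delivery by caesarean hysterectomy, acquired absence of genital organ (hysterectomy" and the procedures as "procedures related to partial excision of uterus or total excision of uterus".
- Bilateral oophorectomy uses Z90.7 again, labelled here "Acquired absence of genital organ(s", with five bilateral procedure codes (LAE 20, LAE 21, LAF 10, LAF 11, LAF 30).
- The cancers are C50*, C53* to C55* and C56*.

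The notes to that table treat a condition as present on any primary or secondary diagnosis, inpatient or outpatient.

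Section 9.7.3.5 gives TTLB its own list. After the live birth itself, the sixth cycle and a switch of drug, it reads "diagnosis of breast, ovarian or uterine cancer, death, emigration (Denmark only) or end of study, whichever occurs first". Hysterectomy and bilateral oophorectomy are not in it.

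Table 1 in 9.3.2 carries "History of any cancer" as a candidate for the propensity score. Section 9.2.1 excludes stimulation for oncological embryo storage, but not women with a cancer history.

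**The concern.** A censoring code should identify the event that the protocol means to censor at. Here several codes reach further than 9.2.3, and one coincides with the outcome. A woman censored by such a code may still have an eligible transfer or birth. MC-CLBR is the most exposed outcome: it is analysed per woman, and 9.7.3.3 assumes no live birth in women who do not return after a failed attempt, so a birth placed after a false exit date could be scored as a failure.

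The mismatch with 9.7.3.5 is a separate fault. Table 5 assigns MC-CLBR and TTLB to the same analysis set (Set 8), and both concern the first live birth. The same woman could have one exit date for one outcome and a different one for the other.

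**Working it through.** The protocol states no figure for censoring or for lost births, so there is nothing to reproduce. The check is mainly textual, with an illustration of scale.

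**Passages side by side**

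| Item | 9.2.3 | 14.3.2 | Result |
|---|---|---|---|
| Z90.7 | Hysterectomy; bilateral oophorectomy | Same code in both rows; label names no organ or side | Can flag a woman with neither operation |
| LCC* | Hysterectomy | Partial excision of the uterus included | Wider than the criterion as worded |
| O82.2 | Hysterectomy | Labelled as a delivery | Censoring can fall on the outcome |
| C50, C53–C56 | Diagnosis | Any primary or secondary record | A repeat record after index qualifies |
| Bilateral oophorectomy | Ends follow-up | Ends follow-up | 9.1.2.1 counts linked frozen transfers in CLBR and MC-CLBR; embryos already frozen remain available |
| Hysterectomy, bilateral oophorectomy | Listed | Coded | Absent from the TTLB list in 9.7.3.5 |

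**Scale**

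Inputs from section 9.5: 19,000 women in the Danish reference cohort (HP-hMG comparison), 75% eligible, comparator MC-CLBR p = 50%, and a detectable difference of 1.5 points. Eligible women: 0.75 × 19,000 = 14,250.

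Assumption, not in the documents: a share f of women is wrongly censored before a birth, is scored as having none, and would otherwise have had the same birth rate as the rest. The observed rate is then p(1 − f). Births not counted are 14,250 × p × f. With equal f in both cohorts a difference d becomes d(1 − f).

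| f | Births not counted | Points off a 50% rate | 1.5-point difference becomes |
|---|---|---|---|
| 0.1% | 7 | 0.05 | 1.4985 |
| 0.5% | 36 | 0.25 | 1.4925 |
| 1% | 71 | 0.50 | 1.485 |
| 2% | 142 | 1.00 | 1.470 |

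The odds ratio at 51.5% against 50% is (0.515/0.485)/(0.5/0.5) = 1.062. At f = 2% it is (0.5047/0.4953)/(0.49/0.51) = 1.061.

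If the frequency differs between cohorts by Δf, the contrast shifts by about p × Δf. A shift of 1.5 points needs Δf = 0.015/0.50 = 3% of women at an MC-CLBR of 50%, or 0.015/0.25 = 6% at 25%. If only 40% of wrongly censored women would have had a later counted birth (also an assumption), a 1-point difference in code frequency shifts the contrast by 0.01 × 0.40 = 0.4 points.

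**The case against.** The strongest reply is that the exit date may not act on these outcomes at all. Section 9.2.3 calls its list general, and then says that each cycle is followed until its outcome is assessed. LBR and CLBR are per-cycle measures, and neither 9.7.3.3 nor 9.7.3.4 says that an exit date cancels a later linked birth. For TTLB, the text of 9.7.3.5 does not censor on the surgical codes and does stop at the first live birth. Births come from the birth registers and the Swedish IVF register, not from O82.2, and the order of same-day events is a programming detail that a SAP may settle. Having Z90.7 in two rows does no harm in itself, since both rows trigger the same action. The appendix also says that its code lists may be revised.

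Much of this stands, and it limits the claim. A reader might infer that real births are lost; the documents support only that they can be, because how the exit date acts on the primary outcomes is not spelled out. A reader might also infer that cancer records from before treatment censor women. They do not: follow-up starts at index, and earlier records belong to the baseline period.

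What survives is what the appendix states outright. Z90.7 reaches women outside both criteria, a delivery is listed as a censoring code, and any repeat cancer record qualifies. The two censoring lists also disagree. Permission to revise makes correction easy; it does not make the present list right.

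**Conclusion.** The point holds as a coding and consistency fault of low severity. The code list is wider than the criteria it serves, and 9.2.3 and 9.7.3.5 must be reconciled. Some eligible births can fall outside follow-up.

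The size is not in the documents and is probably small. Under the assumed range, an equal loss in both cohorts hardly changes the comparison; only a difference in code frequency between cohorts would matter, and it would have to be about 3% of women at an MC-CLBR of 50% to equal the claimed detectable difference of 1.5 points.

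It may be tempting to say that the loss favours one product, because pelvic surgery or cancer history steers the choice of drug. The protocol does not say so: section 9.9.3 describes the drugs as equally recommended and interchangeable in use, while not ruling out baseline differences. Nor does it say how common such surgery is among these women. No direction of bias can be claimed.

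**What to change.** In 14.3.2:

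- Remove Z90.7 from both rows and rely on the organ-specific procedure codes.
- Check that each LCC* code matches hysterectomy as meant in 9.2.3. Which of them leave the uterus in place cannot be read from the protocol.
- Count a live birth on or before the censoring date, or in the same admission, as an event before O82.2 is applied.
- Let only a first-ever breast, ovarian or uterine cancer record after index end follow-up.
- Keep N99.3, whose label is specific to hysterectomy, unless its date is shown to mislead.

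In 9.2.3 and 9.7.3.5, use one reconciled censoring list, and do not end follow-up at bilateral oophorectomy for outcomes that include linked frozen transfers.

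Do not add a rule that a later birth overrides censoring: follow-up would then depend on the outcome, and coded women would stay in only if they succeeded.

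The cost is text and code-list edits, with no new data, best made before outcomes are seen. The downside is that a few true cases recorded only as Z90.7 will be missed. The effect is negligible, because a woman cannot go on to a birth after hysterectomy.

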9.1 Study Design

9.1.1 Design Overview

This is a non-interventional study based on secondary data from national population-based registers in Denmark and Sweden. The study uses a cohort design and is conducted as a comparative effectiveness and safety study with head-to-head comparisons of drugs used for treatment of infertility and in ART. The study drugs are rhFSH-alfa reference product (drug of interest), HP-hMG and rhFSH-alfa biosimilar products (comparator drugs). Together with the rhFSH-alfa reference product, the comparator drugs constitute the main gonadotropins used for COS in ART in both countries of study in recent years. In 2019, the three study drugs comprised 96% of all dispensed prescriptions for gonadotropins in Sweden. In Denmark, the study drugs comprised 89% of all volume sales in the same year¹. Comparisons will be made between the rhFSH-alfa reference product and each comparator drug with respect to clinical effectiveness and safety. Treatment-associated costs will be described. Thus, the newer generation rhFSH-alfa reference product will be evaluated both against the older generation products, HP-hMG, and the newest generation rhFSH-alfa products, the biosimilars.

¹ Publicly available information from each country's online statistical database on pharmaceuticals (*Denmark*: <https://medstat.dk/en>; *Sweden*: https://sdb.socialstyrelsen.se/if_lak/val_eng.aspx). The following ATC codes were used in the search for statistics on sales volumes and number of dispensed prescriptions: G03GA02 (hMG), G03GA04 (urofollitropin), G03GA05 (follitropin alfa), G03GA06 (follitropin beta), G03GA09 (corifollitropin alfa), G03GA30 (combinations). Accessed 10 February 2021.

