9.2.2 Definition of Study Cohorts and Description of Treatments

Among the women included in the study, three study cohorts will be created at the level of the IVF/ICSI stimulation cycle based on which drug the woman received for COS: rhFSH-alfa reference product, HP-hMG or rhFSH-alfa biosimilar product. Only one type of gonadotropin use will be allowed for each stimulation cycle. Hence, cycles where mixed gonadotropin use was observed will not be included in the study. Mixed gonadotropin use may occur for example if, at prescription refill at the pharmacy, the drug (brand) on the written prescription was exchanged for an equivalent drug (same active substance, strength, formulation; therapeutically equipotent).

A woman may contribute maximum five stimulation cycles to the same cohort if she had several cycles with the same study drug. She may contribute cycles to more than one study cohort if she had distinct stimulation cycles with different study drugs. Between stimulation cycles with a study drug, a woman may have received a non-study gonadotropin for COS. History of IVF/ICSI treatment, including with a non-study gonadotropin, will be controlled for in the analysis (in the PS estimation). Overall, no more than five stimulation cycles and only up to the fifth stimulation cycle will be considered in this study, regardless if all cycles were observed in the study period and the type of gonadotropin used for COS.

FET cycles originated from an IVF/ICSI stimulation cycle included in the study will be assigned to the same cohort as that stimulation cycle. FET cycles originated from a stimulation cycle in which one of the study drugs was used but which was not included in the study (e.g., because of PGT), will not be considered. Different methods for cycle linkage will be used for Denmark and Sweden. For Sweden, the IVF register includes information enabling an FET cycle to be linked to the stimulation cycle it originated from. This information is the follicular aspiration date, which is recorded for IVF/ICSI stimulation cycles and FET cycles alike. For Denmark, no such direct link exists in the IVF register.

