9.3.1 Exposure Variables

Exposure of an IVF/ICSI stimulation cycle to rhFSH-alfa reference product (follitropin alfa, ATC code G03GA05), HP-hMG (ATC code G03GA02) or rhFSH-alfa biosimilar product (ATC code G03GA05) will be established based on information from the IVF registers and, primarily, prescriptions dispensed in community pharmacies. While the IVF registers indicate which drug (international nonproprietary name (INN)/ATC) was used for ovarian stimulation, the prescribed drug registers comprise more detail. Additionally, in Sweden, drug information is expected to be available from the Q-IVF starting only from 2019.

Hence, information on the dispensed prescription will include substance name (INN), brand name, ATC code, strength of drug, dosage form, pack size, number of dispensed packages and dispensed amount of drug [in Defined Daily Doses (DDD)]. Using the brand name recorded with the dispensed prescription, it will be possible to distinguish between rhFSH-alfa reference product and rhFSH-alfa biosimilar product. Because information on prescribed daily dose is expected to be incomplete and/or recorded in free-text format, it will not be considered for estimation of total gonadotropin dose.

Using data from the prescribed drug registers, a time window of 30 days before and 35 days after the stimulation cycle index date (27) will be defined to ascertain that gonadotropin monotherapy with a study drug was used for COS. The impact of using a narrower time window for exposure ascertainment will be explored in a sensitivity analysis (see Analysis 1 in Table 8). Any FET cycle(s) linked to an IVF/ICSI stimulation cycle included in the study will be considered exposed to the same study drug as the cycle it originated from.

Total gonadotropin dose will not be considered in the analyses of the comparative study objectives (1-8). However, conditional that the data from the Q-IVF is comprehensive, total gonadotropin dose may be considered for the estimation of drug cost in the descriptive cost analysis for Sweden (see Section 9.7.3.7), albeit for a limited portion of the study period.

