14.3 Additional Information

All code lists included below may be subject to amendment or revision during study conduct.

14.3.1 Outcome variables (Section 9.1.2): Diagnosis and Procedure Codes for Definition and Databases for Identification

Outcome	Code for identification ⁺	Comment	Source for identification
Primary outcome			
Live birth	N/A		DMBR, SMBR, Q-IVF
Secondary outcomes			
Clinical pregnancy	ICD-10: O00 NOMESCO procedure codes: MCB 00, LAA 20, LBC*	Intrauterine pregnancy ascertained in the DIVF and Q-IVF. ICD-10: Ectopic pregnancy NOMESCO procedures: laparotomy and delivery of extrauterine fetus, percutaneous or transvaginal injection into ovarian pregnancy, tube conserving operations for tubal pregnancy	DIVF, Q-IVF, DNPR, SNPR
Ongoing pregnancy	ICD-10: O03, O04, O05, O06 [#] NOMESCO procedure codes: LCH*	Delivery and gestational age at delivery ascertained in the DMBR and SMBR. For Sweden, miscarriage and induced abortion† will be ascertained in the SNPR and Q-IVF. ICD-10: spontaneous abortion, medical abortion, other abortion, unspecified abortion NOMESCO procedures: procedures related to termination of pregnancy	DMBR, SMBR, DNPR, SNPR, Q-IVF
Oocytes retrieved	N/A	Ascertained using information recorded in the DIVF and Q-IVF.	DIVF, QIVF
Embryos transferred			
Embryos cryopreserved			
Implantation			
Pregnancy loss	ICD-10: O03, O04, O05, O06 [#] NOMESCO procedure codes: LCH*	ICD-10: spontaneous abortion, medical abortion, other abortion, unspecified abortion NOMESCO procedures: procedures related to termination of pregnancy	DNPR, SNPR, Q-IVF

Outcome	Code for identification ⁺	Comment	Source for identification
		For Sweden, miscarriage and induced abortion† will be ascertained in the SNPR and Q-IVF.	

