⁺Country-specific adaptations may be made at the data permit stage. Conditions defined by ICD-10 codes are considered present if there was a record of a primary or secondary diagnosis in the national (patient) registers (outpatient or inpatient care)]. Similarly, procedures defined by NOMESCO codes are considered to have been performed if there was a record in the national patient registers (outpatient or inpatient care).

*All ICD-10 or procedure subcodes are included.

[#] Identification in the national patient registers, as opposed to the cancer registers, is considered sufficient for the intended use in this study.

14.3.3

Exposure (Section 9.3.1) and Other Variables (Section 9.3.2): Codes for Definition

Variable	Code ⁺	Comment
Type of gonadotropin used for COS, including study and non-study drugs (ATC codes)		
Follitropin alfa	G03GA05	Distinction between rhFSH-alfa reference and biosimilar products possible using brand name
Human menopausal gonadotropin	G03GA02	
Urofollitropin	G03GA04	
Follitropin beta	G03GA06	
Corifollitropin alfa	G03GA09	
Combinations (of recombinant hormones)	G03GA30	
GnRH drugs (ATC codes)		
Nafarelin	H01CA02	
Ganirelix	H01CC01	
Cetrorelix	H01CC02	
Buserelin	L02AE01	
Drugs used for ovulation triggering (ATC codes)		
Chorionic gonadotropin (human urinary)	G03GA01	
Choriogonadotropin alfa (human recombinant)	G03GA08	
Drugs used for luteal phase support (ATC codes)		
Progesterone	G03DA04	Dosage form determined by other information recorded with the dispensed prescription
Fertility-related medical history and other clinical characteristics (ATC, ICD-10 and procedure codes)		
Obesity	ICD-10: E66*	
Bariatric surgery	NOMESCO procedure code: JDF*	Bariatric operations on stomach: Operations for morbid obesity and intestinal bypass operations
Type 1 diabetes mellitus	ICD-10: E10*	
Type 2 diabetes mellitus	ICD-10: E11*	
Thromboembolic events	ICD-10: I21*, I26*, I63*, I65*, I66*, I67.6, I74*, I80.1, I80.2, I80.3, I80.8, I80.9, I81*, I82*, H34*, K55.0, O22.3, O22.5, O22.8, O22.9, N28.0	Pulmonary embolism, cerebral infarction, thromboembolic disease unspecified, thromboflebitis (excluding superficial), deep thrombosis in pregnancy, venous complication in pregnancy, other
Thrombosis prophylaxis	ATC: B01A*	Antithrombotic agents, including vitamin K antagonists, heparin, platelet aggregation inhibitors, enzymes, direct thrombin inhibitors, direct factor Xa inhibitors, other

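### As printed, the six-code gonadotropin list in Protocol 14.3.3 cannot fully enforce the monotherapy rule: a study drug dispensed together with an unlisted gonadotropin would be classified as monotherapy

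*Protocol*

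**What the plan says.** **The rule.** Protocol 9.2.2 states: "Only one type of gonadotropin use will be allowed for each stimulation cycle". It adds that "cycles where mixed gonadotropin use was observed will not be included in the study". In 9.3.1, a window from 30 days before to 35 days after the start of the cycle "will be defined to ascertain that gonadotropin monotherapy with a study drug was used for COS". The main source is the prescribed drug registers.

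**The codes.** Section 14.3.3 gives the codes for the exposure variables of 9.3.1. Under "Type of gonadotropin used for COS, including study and non-study drugs (ATC codes" it lists follitropin alfa (G03GA05), hMG (G03GA02), urofollitropin (G03GA04), follitropin beta (G03GA06), corifollitropin alfa (G03GA09) and "Combinations (of recombinant hormones", coded G03GA30. Chorionic gonadotropin (G03GA01) and choriogonadotropin alfa (G03GA08) appear only as triggers. A footnote to the table infers drug use from dispensings that match the listed codes.

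**The market shares.** Section 9.1.1 reports: "In 2019, the three study drugs comprised 96% of all dispensed prescriptions for gonadotropins in Sweden". The Danish figure is 89% of sales volume. The footnote gives the codes searched: "G03GA02 (hMG), G03GA04 (urofollitropin), G03GA05 (follitropin alfa), G03GA06 (follitropin beta), G03GA09 (corifollitropin alfa), G03GA30 (combinations".

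**Room for change.** Section 14.3 opens with: "All code lists included below may be subject to amendment or revision during study conduct". The table footnotes also allow country-specific adaptation at the data permit stage.

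**The concern.** The rule is written for gonadotropins in general, but the instrument that applies it is six single codes. Mixed use leads to exclusion only where it is observed, and a product outside the list is not observed. The list recognises a fixed combination of recombinant hormones, yet has no means of seeing a second hormone that is dispensed separately and falls outside the six codes.

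This matters most for the comparison with HP-hMG. Section 7 describes hMG as a mixture of FSH, LH and hCG. A reference-product cycle supplemented with separate LH would sit in the recombinant FSH cohort while sharing a feature that sets hMG apart.

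Three other parts of the plan need to know which gonadotropin was used, and would share the gap if they draw on the same list:
- the propensity-score covariate for earlier stimulation with a non-study drug (Table 1);
- censoring of time-to-live birth when a woman changes stimulation drug (9.7.3.5);
- the Danish rule that links or excludes a frozen embryo transfer according to whether the preceding cycles used the same gonadotropin (9.2.2).

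**Working it through.** No figure in the protocol is contested, so the check is mainly a comparison of sections.

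1. **Does the list cover the class?** It has six codes for stimulation and two for triggers, all within G03GA. None carries a wildcard and none is labelled as a separate LH product. Elsewhere the same table takes whole ATC groups: A10* for antidiabetic drugs, B01A* for thrombosis prophylaxis, and the groups N05A, N05B, N05C and N06A for psychotropic drugs. Group-level screening is therefore already used for covariates, but not for the exposure.

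2. **Is the screen tied to the list?** Section 14.3.3 is titled as the code definitions for the exposure variables, and its footnote ties drug use to the listed codes. No other code set for gonadotropins is given. A study drug plus an unlisted gonadotropin in the window would match one code only, and the cycle would be kept as monotherapy.

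3. **Would another source catch it?** The IVF registers record a stimulation drug, but 9.3.1 expects this for Sweden only from 2019, and 9.9.2 says the information is not comprehensive in either country. For most of 2010-2020, Sweden depends on the dispensing codes.

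4. **Would a planned analysis reveal it?** Sensitivity analysis 1 (Table 8) narrows the window to 15 days on either side; it does not change the codes. The 96% and 89% shares use the same six codes as denominator, so they cannot show that unlisted use is negligible.

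5. **How large could the effect be?** The protocol gives no share of co-treated cycles. As an illustration only, let a fraction f of the reference cohort be co-treated and have the same outcome rate as HP-hMG. Then

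   observed difference = true difference × (1 − f).

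   With a true difference of 1.5 points, which 9.5 gives as the minimum detectable difference for this comparison:
   - f = 1%: 1.5 × 0.99 = 1.485
   - f = 5%: 1.5 × 0.95 = 1.425
   - f = 10%: 1.5 × 0.90 = 1.35
   - f = 20%: 1.5 × 0.80 = 1.20

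   The values of f are assumptions. If co-treated women differ in prognosis from the rest of the cohort, the shift could go either way.

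**The case against.** The strongest reply is that the list is not closed. Section 14.3 allows all code lists to be revised, and the footnotes allow national adaptation. The monotherapy rule names no codes, and Table 8 says the window is meant to capture all relevant gonadotropin prescriptions. Operational code sets are also often left to the analysis plan. This stands to the extent that the defect belongs to the list as printed and can be repaired without changing the design. It does not remove the point: permission to amend plans no change, and here the protocol itself fixed the exposure codes.

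The second reply is that nothing in the protocol shows that separate LH, or any other unlisted gonadotropin, was dispensed in Denmark or Sweden. That stands. A gap in the ATC numbering is not evidence of a product in use.

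Several stronger readings are tempting, and the protocol does not support them:
- A reader might infer that reference-product live birth rates are understated because added LH goes to poor responders. The protocol says nothing about who receives it, so the direction of bias is not established.
- A reader might treat 1.5 points as the live birth difference of interest per cycle. In 9.5 it is a minimum detectable difference, calculated for the multiple-cycle cumulative rate per woman at a 50% comparator rate.
- A reader might conclude that the 96% and 89% shares are too high. That follows only if unlisted products were sold. The shares are also descriptive; the study size rests on other sources.
- A reader might call the list a contradiction of the rule. It is an omission.

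A last objection concerns the remedy. Dropping cycles because of an add-on dispensed after stimulation began conditions on a later event and could act mainly on the recombinant cohorts. That is a fair caution. The existing rule already does this for listed products, so the answer is to make the exclusions visible by cohort.

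**Conclusion.** The point holds as a gap between rule and instrument. If the printed list is the screen, the monotherapy criterion is not fully enforced, and no planned analysis would expose the failure. The threat is clearest for the contrast with HP-hMG. Frequency, size and direction cannot be derived from the protocol. Under the assumed dilution the loss is small unless co-treatment is common: 0.075 points out of 1.5 at 5% (1.5 − 1.425) and 0.15 at 10% (1.5 − 1.35). The case for change rests on how little it costs to make the list match the protocol's own criterion, not on a demonstrated bias.

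**What to change.** Before data extraction, define the screen at class level. Any G03GA dispensing in the exposure window other than the assigned study product counts as mixed or non-study use under the existing rule, with G03GA01 and G03GA08 excepted as ovulation triggers. Use the same definition for history of stimulation with a non-study drug, for censoring at switch in the time-to-live-birth analysis, and for the Danish frozen-transfer linkage rule. Recheck the 96% and 89% shares against the full class and restate them only if they change.

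The cost is one change to the code list. The prescribed drug registers record the ATC code of each dispensed drug, but the data application must request the whole class. Timing matters: the milestones put Danish extraction from August 2021 and Swedish extraction from January 2022. The downside is that a small number of cycles leave the monotherapy cohorts. Because add-on products may be dispensed after stimulation starts and may affect mainly the recombinant cohorts, report the number excluded for this reason in each cohort.
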